#### 14.5 Safety analysis

Local ear irritation/pain and dermatitis will be recorded. Non-compliance and the reasons for failure to comply will be recorded.

#### 14.6 Procedure(s) to account for missing or spurious data

As the primary outcome uses routinely captured data stored by Barts Health EPR, there is minimal risk of missing blood pressure-related data. Heart rate data will be captured by dedicated Holter monitors provide by the Chief Investigator. Any missing data will not be inputed. Sensitivity analyses to assess the robustness of study results if there are missing primary outcome data will be undertaken. This pilot study will assess data completeness to inform decisions about missing data for a future main trial. Analysis will use all participants with available endpoint data. The level of missing data will be tabulated for each outcome, presenting the number of subjects with a data record and number with missing data, separately by trial arm. Each endpoint will be analysed on a complete case basis. For continuous variables, distributional assumptions will be hard to assess with the small sample size for this pilot study. However, if any continuous endpoint variables appear to seriously violate distributional assumptions or very extreme outliers observed, then non-parametric alternative approaches to analysis will be undertaken in such cases.

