# 2.3.2 Secondary endpoint(s)

- Systolic blood pressure variability from blood pressure measured in each patient during the first 24 hours from the start of mechanical thrombectomy.
- Disatolic blood pressure variability from blood pressure measured in each patient during the first 24 hours from the start of mechanical thrombectomy.
- Heart rate variability measured during each period of transcutaneous autonomic neuromodulation.
- NIH Stroke Scale (NIHSS) measured in each patient before the start of mechanical thrombectomy and 24 hours after the start of procedure.
- Clinically recorded arrhythmias in each patient during the first 24 hours after the start of mechanical thrombectomy.
- Absolute levels of serum high-sensitivity troponin-T levels measured before the start of the first transcutaneous autonomic neuromodulation and at the end of the second transcutaneous autonomic neuromodulation.

[figure not shown]

\* please see Appendix A for details on the assessment of primary and secondary outcomes

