# 14.2 Analysis of participant populations

The main analyses of the primary and secondary endpoints will be conducted on an intention-to-treat population, consisting of all participants with available data based on the trial group to which they were randomized to, irrespective of their compliance to their prescribed treatment as specified in the protocol. For continuous endpoints, mean, and SD, and number of participants with available data will be presented along with estimated crude and adjusted mean differences between trial arms. Binary endpoints will be shown as the number with each endpoint and total number in each group along with the percentage. For binary endpoints, the crude and adjusted odds ratios (ORs) will be estimated.

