#### 14.4 Secondary endpoint analysis

Blood pressure and heart rate variability measures will be analysed by repeated measures ANOVA (significance set at p<0.05), analysed in the same way as for the primary endpoint, as detailed above. Specifically, this entails systolic and diastolic blood pressure variability (standard deviation, average real variability, successive variation and residual standard deviation) plus time and frequency domain measures of autonomic cardiac modulation in the first 24 hours after mechanical thrombectomy. The following secondary outcomes will be reported but not subject to statistical testing.

- Blood pressure variability in the first 24 hours from start of mechanical thrombectomy
- Heart rate variability in the first 24 hours from start of mechanical thrombectomy
- NIH Stroke Scale (NIHSS)
- Arrhythmias
- Myocardial injury

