the sample size is derived from data reported from the secondary analysis of the BEST study, which examined blood pressure variability and neurologic outcome after endovascular thrombectomy.[1] An adjusted sample size of 36 patients is required to have a 90% chance of detecting, as significant at the 5% level, a decrease in the coefficient of variation in systolic blood pressure from 15±4mmHg in the sham group to 10±4mmHg in the VAN group [assuming 5% non-compliance rate in each group]

Randomisation procedure

Randomisation will occur before the surgical procedure is due to start. Block randomisation (blocks of 4) will be undertaken (STATA). To enter a patient into the VANS trial, research staff at the site will log on to a secure web-based randomisation and data entry platform hosted by Queen Mary University of London and complete the patient's details to obtain a unique patient identification number and allocation to a treatment group. A patient's treatment group allocation will only be revealed to the person performing randomisation.

4. Analysis methods for VANS

General analysis principles

Analyses will follow the intention-to-treat principle: all randomised patients with a recorded outcome will be included in the analysis and analysed according to the treatment to which they were randomised [2, 3]. Patients will be included in the analysis, regardless of whether the treatment they received was compliant with the protocol. Missing data for baseline covariates to be included in the analysis model will be accounted for using mean imputation for continuous variables and the missing indicator approach will be used for missing data for categorical variables [4, 5].

For the analysis of the primary outcome, each secondary outcome, and all process measures, we will present the following information:

- The number of patients included in each analysis, by treatment group
- A summary statistic of the outcome (e.g. mean (SD), number (%)), by treatment group
- The estimated treatment effect
- A 95% confidence interval for the estimated treatment effect
- A two-sided p-value

For all analyses, a significance level of 5% will be used.

Representativeness of patients

All participating sites have been asked to keep a log of eligible patients not recruited to the trial. Reasons for non-participation will be categorised and summarised. Participation in the trial, treatment allocation and completeness of follow-up will be illustrated by a CONSORT flow diagram [6].

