 BPV formulae are provided in supplementary data. These measures take into account the distribution and linear trends of BP in an effort to reduce the dependency of BPV on mean BP level.
- 2. Autonomic cardiac modulation in the first 24h after mechanical thrombectomy (Holter monitoring).
- 3. Neurological recovery will be reported by recording serial NIH Stroke Scale (NIHSS) scores, an FDA-approved primary outcome measure for stroke in early phase II trials before and 24h after mechanical thrombectomy.[8]

Exploratory objectives

Biomarkers for risk of infection (whole blood leukocyte transcriptomic changes after incubation at 37°C with sterile saline or 100ng/ml lipopolysaccharide for 4h), infections within 7 days of MT and myocardial injury (high-sensitivity troponin) will also be quantified. Cardiac injury will be assessed by measuring high-sensitivity troponin T on admission and 24h after MT.

Sensitivity analysis

For patients discharged before the repeat stimulation intervention or repatriated to referring centres before the repeat intervention, we will undertake a sensitivity analysis. The primary analysis will be repeated once assuming that all patients in the continue group with missing outcomes did not have BPV >20. The analysis will then be repeated again with the opposite assumptions. This will then give the absolute range of how much the results could change if the data were complete. This will also assess the robustness of our analysis of the primary outcome under the assumption that data is missing-not-at-random (MNAR).

5. Other analyses, data summaries and graphs

Clinical management

Clinical management for the treatment allocation will be summarised but not subjected to statistical testing. Numbers (%) and means (SD) or medians (IQR) will be provided separately for each principal exposure group:

- Thrombectomy technique
- General Anaesthesia/ Sedation
- Endotracheal tube inserted?
- Did the patient have any arrhythmias
- Intraoperative hypotension
- Planned level of care.

Process measures

Summary measures will be presented separately for each treatment allocation. All patients with recorded data will be included in the summary. Formal statistical analysis will not be performed. Patient status at follow up (alive/dead; home/hospital) seven days after MT will be presented as number (%).

Safety analyses

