HF, power				
HF, peak				
DFA1				
DFA2				

Table 6. Process/ exploratory measures.

	ACTIVE	SHAM
NIH Stroke Scale (NIHSS) 24h after mechanical thrombectomy (delta change from admission)		
Health status 7 days after mechanical thrombectomy.		
Alive		
Troponin change from admission (delta change from admission)		

Table 7:Adverse events

Adverse Events - no. (%)	active	sham
Patients with ≥ 1 adverse event		
Total number of adverse events		
Type of adverse event		
Cardiac arrythmia		
Local skin irritation		
Other

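### A patient who dies before the 24 h NIHSS is left out under the complete-case rule, so the NIHSS summary describes survivors only

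*Protocol*

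**What the plan says.** Protocol section 2.3.2 makes NIHSS a secondary endpoint, "measured in each patient before the start of mechanical thrombectomy and 24 hours after the start of procedure". It is the only neurological outcome in either document. SAP section 4 (Analysis of secondary outcomes, item 3) says "Neurological recovery will be reported by recording serial NIH Stroke Scale (NIHSS) scores", and SAP Table 6 shows the change from admission by arm.

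Three statements decide who enters that summary:

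- Protocol 14.2 defines the intention-to-treat population as "consisting of all participants with available data based on the trial group to which they were randomized to".
- Protocol 14.6 says "Any missing data will not be inputed" and "Each endpoint will be analysed on a complete case basis".
- SAP section 4 (General analysis principles) says "all randomised patients with a recorded outcome will be included in the analysis". Its imputation rules cover baseline covariates only.

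The missing-data sensitivity analyses in both documents concern the primary outcome. SAP Appendix 1 sets missing-value rules for troponin, infection and day-7 status, but has no entry for NIHSS.

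**The concern.** A 24 h score absent because the patient has died is not missing in the usual sense. There is no unobserved value to recover, and the outcome is worse than any score a living patient could have. Treating it like a lost form restricts the summary to a group defined after randomisation.

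Two consequences follow. Absolute recovery in an arm looks better than it was whenever a patient in that arm dies early. If early deaths differ between arms, the comparison leans towards the arm with more of them. Protocol 13.1 describes the trial as a pilot for a larger efficacy trial, so a survivors-only neurological signal could carry over into the planning of that trial.

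**Working it through.** **The plan's own figure.** The stated sample size rests on systolic blood pressure variability. Inputs: means of 15 and 10, 5% non-compliance per group, two-sided 5% level and 90% power (protocol 13.1, SAP sections 3 and 4), and SD 4 (SAP section 3). Reading non-compliance as dilution, the effect is 5 × (1 − 0.05 − 0.05) = 4.5. A two-sample t-test then needs 18 per arm, 36 in total, with power 90.6%. The figure reproduces and does not involve NIHSS.

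**What happens to an early death.**

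1. The patient has an admission NIHSS but no 24 h score, so no change score can be formed.
2. Protocol 14.2 and SAP section 4 require an available or recorded outcome, so the patient is outside the NIHSS analysis set.
3. Protocol 14.6 rules out imputation, and no sensitivity analysis covers NIHSS.
4. No score, rank or composite for death is given anywhere, so nothing brings the patient back.

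**Size per death.** With 1:1 allocation (protocol 6.3), 36 patients give 18 per arm. One, two or three deaths in an arm remove 1/18 = 5.6%, 2/18 = 11.1% or 3/18 = 16.7% of it. If a death is given a value *g* points above the survivor mean, the arm mean moves by *g*/18:

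- *g* = 10: 10/18 = 0.56 points
- *g* = 20: 20/18 = 1.11 points
- *g* = 35: 35/18 = 1.94 points

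The range of *g* is assumed. For the change score in Table 6 the same formula holds with *g* measured on the change scale, where it also depends on the dead patient's admission score.

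**How often it could arise.** The documents give no 24 h death risk *r*, so the values below are assumptions, taken as equal in both arms.

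- Expected deaths = 36*r*.
- P(at least one) = 1 − (1 − *r*)^36. At 1%: 1 − 0.99^36 = 0.304.
- P(unequal between arms) = 1 − Σ P(*k* deaths among 18)². At 1%: 1 − (0.8345² + 0.1517² + 0.0130²) = 1 − 0.720 = 0.280.

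| Assumed *r* | Expected deaths in 36 | P(at least one) | P(unequal) |
|---|---|---|---|
| 1% | 0.36 | 30% | 28% |
| 3% | 1.08 | 67% | 56% |
| 5% | 1.80 | 84% | 67% |

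The third column bears on the absolute summary and the fourth on the comparison between arms.

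**Is NIHSS tested?** Protocol 14.4 lists it under "The following secondary outcomes will be reported but not subject to statistical testing". SAP Table 6 places it among process and exploratory measures without a p-value column. SAP section 4, however, promises an effect estimate, a 95% confidence interval and a two-sided p-value for every secondary outcome. These statements do not agree.

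**The case against.** The strongest reply is that little is at stake. NIHSS is secondary, and on the protocol 14.4 and Table 6 reading it is only described, in a 36-patient pilot. Deaths are not hidden: protocol 14.6 tabulates missing data by outcome and arm, day-7 status is given by arm, serious adverse events are reported by arm, and a CONSORT diagram shows completeness of follow-up. Early deaths may be few, and survivors with severe deficits are still scored.

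Most of this stands, and it limits the weight of the point. It does not remove it, because none of those outputs can be tied to the NIHSS row. The missing-data table is not said to give reasons, and the SAP itself expects some patients to be discharged or repatriated early, so an absent score could mean death or transfer. Table 6 counts patients alive at day 7 but not deaths before 24 h, and the derived day-7 variable in SAP Appendix 1 puts death and still being in hospital in one category.

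A reader might infer three stronger things that the documents do not support:

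- That deaths disappear from the trial report. They leave only the NIHSS summary.
- That the plan scores an early death as no change. The patient is excluded; no value is entered.
- That the comparison will point the wrong way. That needs unequal early deaths. Under equal risks any imbalance is chance and could favour either arm.

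It is also fair that ranking deaths worst does nothing for patients transferred before 24 h. They remain a separate source of selection.

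**Conclusion.** The point holds in a limited form. As written, the NIHSS summary covers survivors only. It is too favourable in absolute terms if anyone dies before 24 h, and the comparison is biased if early deaths are unequal between arms. The shift is about 0.6 to 1.9 points in an arm mean per death, resting on an assumed gap of 10 to 35 points; its likelihood rests on a death risk that the documents do not give.

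If NIHSS is only described, the harm is a misleading summary. If the SAP's general principle governs, the estimate, interval and p-value are affected too. Nothing here touches the primary endpoint or the sample size of 36. The gap is worth closing before unblinding, so that the handling of deaths is not chosen once it is known in which arm they fell.

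**What to change.** In the SAP:

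1. State that death before the 24 h assessment ranks worse than any recorded score, and add an NIHSS entry to Appendix 1 saying so.
2. Summarise NIHSS by arm with a median and IQR that include those deaths.
3. Reconcile protocol 14.4, SAP section 4 and Table 6 on whether NIHSS is tested. Add a rank-based estimate and test only if a test is kept.
4. Add a Table 6 row for deaths before 24 h by arm, and a separate count of scores missing for other reasons such as repatriation.
5. Keep the survivors-only change from admission as a supportive summary, labelled as such.

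The cost is SAP wording and table rows, recorded in the SAP revision history as protocol 14.7 provides, plus a protocol clarification if step 3 keeps a test. The reason for each absent 24 h score has to be identifiable. Sample size and patient procedures do not change. The small downside is that a rank summary is less direct to interpret than a mean change.

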#### 14.7 Other statistical considerations

Any changes to the original analysis plan will be recorded in the SAP (SAP revision history) along with dates, updated SAP version number and description of and reasons for the changes.

#### 15.0 Data handling and record keeping

#### 15.1 Source data and source documents

ISO14155 GCP section 3.47, defines source data as "all information in original records, certified copies of original records of clinical findings, observations, or other activities in a clinical investigation, necessary for the reconstruction and evaluation of the clinical investigation." ISO14155 GCP section

3.48, defines source document as "original or certified copy of printed, optical or electronic document containing source data." To enable review, monitoring, audit and/or inspection of study source data, the Principal Investigator agrees to keep records of all participating participants. Example of these original documents, and data records include (but are not limited to) electronic participant records/clinical notes, original signed consent form, crib sheets(s), participant trial file, participant diary, participant logbook, recorded data from automated instruments, laboratory notes, questionnaires (paper and/or electronic), evaluation checklists, accountability logs, copies or transcriptions (certified after verification as being accurate and complete) and records kept at the laboratories involved in the trial.

A Source Data Agreement (SDA) will be established by Site team and Sponsor monitoring team detailing a full list of all trial source data documents including what comprises source data, corresponding source data documents and its location. The SDA will be held in the ISF and TMF. All source data will be collated by the Investigation site team.

JRMO Clinical Trial Monitor or delegate will have access to source data and source documents for source data verification aspects of monitoring. Direct access will also be granted to authorised representatives from the Sponsor and the regulatory authorities to permit trial-related monitoring, audits, and inspections.

Study research staff will have access to the patient record to record trial outcomes. Holter data labelled by unique trial IDs will be analysed using Kubios software for offline analysis. Direct access will be granted to authorised representatives from the Sponsor, host institution, and the regulatory authorities to permit study-related monitoring, audits, and inspections.

#### 15.2 Case Report Forms (CRFs)

Pseudonymised trial data will be captured electronically via electronic case report form (eCRF). The CRF will be designed by the database manager in the Critical Care and Perioperative Medicine Research group with input from the Chief Investigator in accordance to Sponsor requirements. Only trial data including safety events that will be used for statistical analysis will be collected. Chief Investigator, Sub-Investigator(s) and Investigation site team are permitted to record on the eCRF(s). The eCRF will be built and managed on a secure web application.

Direct access to eCRF will be restricted, with only delegated and authorised users will be issued with (trial role related and defined) access to the eCRF. Each user will be assigned specific user roles and rights, and this will be reflected on the respective delegation log.

#### 15.3 Data capture

Source data will be collected by the investigators or the research nurses and captured in an eCRF with electronic signatures and an audit trail. All source data is obtained from site medical notes including the electronic patient record. Direct access to the database will be restricted to named users only. The eCRFs will be completed by the Investigator or suitably trained research staff, as designated in the site

delegation log, as accurately and completely as possible throughout the study. Source data will be reviewed as part of the source data verification during site monitoring.

#### 15.4 Transferring and transporting data

All data must be handled in accordance with the Data Protection Act (2018) and General Data Protection Guidelines. No data will be transferred outside of the EEA. Identifiable information will not be stored, transported on any portable device (e.g. laptops, memory sticks, CD /DVDs) unless it is encrypted and will not be sent electronically; if it is not subject to end-to-end encryption. Barts Health Participant Identifiable Data (PID) will not be taken out of Barts Health without participant consent.

#### 15.5 Data Management

Source data verification will be conducted in the eCRF. Final sign-off by the site Principal Investigator will be undertaken. A single final data lock will prevent changes, to protect the final data set. The final dataset will be exported from the study database for analysis by the trial statistician. A trial specific Data Management Plan will be developed by the Coordinating team detailing all key methods of data management for collecting, recording and handling of trial data.

#### 16.0 Confidentiality

The Chief Investigator will be the data custodian for all data generated during the study. The Chief Investigator and the study team will ensure that all participants' identities are protected at every stage of the study. To ensure this, at time of consent each participant will be allocated a unique screening number by the coordinating team before undergoing any screening procedures. The Principal Investigator is responsible for protecting the identity of participants at their site. Participants will be referred to only by their unique trial identifier whenever data is transferred outside of the site, and in all correspondence between the site and the coordinating centre, co-investigators, Sponsor, or anyone associated with the study. No participants will be individually identifiable from any publications resulting from the study. Information regarding study participants will be kept confidential and managed in accordance with the Data Protection Act (2018), the UK Policy Framework for Health and Social Care Research and Research Ethics Committee approval. All study data will be stored and archived in line with the Medical Device Regulations 2002 and subsequent amendments and the Data Protection Act, as described in JRMO SOP 20 Archiving.

### 16.1 De-identification of participants

A screening log will be maintained at site throughout the study, detailing the potential participant's initials to allow their identification by relevant site staff. Once the participant has completed screening procedures and is enrolled onto the study, they will be allocated a unique trial identifier by the coordinating team. All data will be de-identified before it is used. Medical record numbers will be the only identifiable information collected from the participants stored within the eCRF to facilitate location of the patient within Barts Health, Royal London Hospital by research staff. Other Identifiable data will be de-identified, kept secure, and maintained by the creation and use of a unique identifier

for each participant. Encrypted data will be password protected with limited access afforded to the minimum number of individuals necessary for quality control, audit, and analysis.

